8. STATISTICAL METHODOLOGY

8.1. Study Subjects

8.1.1. Subject Disposition

Subject disposition will be summarized on the SAF and listed on the enrolled subjects.

8.1.2. Analysis Populations

Analysis populations including the inclusion and exclusion criteria deviation at screening will be summarized and listed on the all enrolled subjects.

8.1.3. Administration of Investigational Product

Administration data will be summarized and listed on the SAF.

8.1.4. Demographic and Other Baseline Characteristics

The following demographic and other baseline characteristics will be used.

	category	descriptive
Sex	Male, Female	
Age at informed consent(years)		Yes
Height(cm)		Yes
Weight(kg)		Yes
BMI(kg/m ²)		Yes
Race	Japanese	
Medical History	No, Yes	
Complication	No (if status of medical history is 'Ongoing'), Yes (if otherwise)	
Concomitant Medication	No, Yes	
Allergic History (including drug allergies)	No, Yes	
Drinking Status	No (if 'Never'), Yes (if otherwise)	
Smoking Status	No (if 'Never'), Yes (if otherwise)	

Demographic and other baseline characteristics will be summarized and listed on the SAF.

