Urine sampling for edaravone ^{d)}		←												→				

- a) The diet menu in period V will be determined based on the PK data collected from period I to IV.
- b) The dosing time after a meal in period V will be determined based on the PK data collected from period I to IV.
- c) Assess serious adverse events beginning after informed consent is obtained. Survey of other adverse events will be started after administration of the investigational product is started.
- d) Urine volume is measured for each void. A portion of the urine is collected, dispensed into a tube containing stabilizer, and stored frozen. The urine is forced to void at 24-hour intervals.
- e) At the time of withdrawal, the same tests will be performed as those of the end-of-study assessment.
- f) In the F: Dosing 4 hours after light meal, tests/observations are conducted 46 hours after administration of the investigational product.

Confidential

Test items	Description
Demographic and other baseline characteristics (subject characteristics)	Sex*, race*, date of birth*, body height*, body weight, BMI**, medical history*, complications*, history of allergies (including drug allergies) *, alcohol consumption*, smoking status*
Interview/physical examination	Interview and physical examination
Vital signs	Blood pressure (supine), pulse rate, body temperature (axillary)
12-lead ECG	HR, QTcF interval, PR interval, QT interval, RR interval, QRS interval, findings
Laboratory tests	Hematology
	Hemoglobin, hematocrit, red blood cell count, white blood cell count, platelet count, MCH, MCHC, MCV, differential white blood count
	Biochemistry
	Na, K, Cl, Ca, inorganic phosphorus, urea nitrogen, creatinine, uric acid, total bilirubin, direct bilirubin, ALT, AST, γ -GTP, ALP, LDH, CK, amylase, total cholesterol, triglycerides, LDL-C, HDL-C, total protein, albumin, glucose
Coagulation test	Prothrombin time, activated partial thromboplastin time
	Urinalysis
Serological tests*	HBs antigen, serological test for syphilis, HCV antibody, HIV antigen/antibody
Drug/alcohol abuse screening*	Urine drug abuse screening (phencyclidine, cocaine, barbiturates, tetrahydrocannabinol, benzodiazepines, amphetamine/methamphetamine, morphine-based anesthesia), measurement of breath alcohol level

*: To be performed only at screening.

**: To be performed at screening and Day -1 (hospitalization).

***: To be performed only for female subjects. At screening, on Day -1, (hospitalization) and at the end-of-study assessment.

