- c) A case which requires hospitalization in a hospital or clinic, or extension of a hospitalization period for treatment
- d) Disability
- e) A case which may lead to disability
- f) A case of a serious disease, according to the cases listed in a) through e)
- g) A congenital disease or abnormality in later generations

4) Relationship to the investigational product

The investigator (or subinvestigator) will assess whether any “reasonable relationship” exists between an AE and the investigational product. The assessment will include such factors as the natural course of complications or underlying diseases, combination therapies, risk factors other than the investigational product, and the temporal relationship of the event onset to the investigational product administration (e.g., recurrence of the event after reintroduction of the investigational product, disappearance of the event after discontinuation of the investigational product). An AE that is judged as “reasonably related” to the investigational product is defined as an ADR.

1. Reasonably related
2. Not reasonably related

5) Outcome

The outcome of AEs will be graded on the following 6-point scale.

1. Recovered
2. Recovering
3. Not recovered

Confidential

4. Recovered with sequelae

5. Death

6. Unknown

6) Date of outcome

The date of outcome will be defined according to the outcome, as shown below.

Recovered: The date on which a subject has recovered. However, if the date of recovery cannot be determined, the date of confirmation or judgment of recovery will be used.

Recovering: The date of confirmation or judgment of recovering

Not recovered: The date of confirmation or judgment of not recovered

Recovered with sequelae: The date of confirmation or judgment of recovered with sequelae

[figure not shown]
Death: The date of death. However, if the date of death cannot be determined, the date of confirmation or judgment of death will be used.

Unknown: If the date of outcome cannot be determined due to the subject's death from a cause other than the AE, the date of death will be used. For other cases, the date of confirmation or judgment will be used.

During hospitalization in this study, the time of outcome will also be determined according to the above criteria. If the time of outcome cannot be determined, the time of confirmation of the outcome will be used.

Confidential

7) Follow-up

- Period (1) consists of 7 days. During Period (1), AEs will be assessed.

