13.4.1 Analysis of demographic characteristics and other baseline characteristics of the

Confidential

subjects

Regarding the following items about demographic characteristics and other baseline characteristics, frequency and percentage will be calculated for the discrete values, and descriptive statistics will be calculated for the numerical data. The calculation will be made for each group.

Assessment item: age, sex, height, body weight, BMI, race, medical history, complications, and concomitant medications

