8.1.5. Medical History and Allergic History

Medical history and allergic history will be listed on the SAF.

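### The SAP's coding of the baseline Complication row is reversed: an ongoing condition is coded No and everything else Yes

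*SAP*

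**What the plan says.** Protocol 13.4.1 requires frequencies and percentages of baseline characteristics, calculated for each group, and names complications as an item separate from medical history: "Assessment item: age, sex, height, body weight, BMI, race, medical history, complications, and concomitant medications". The test-items table in Protocol 9.1 makes the same separation: "medical history*, complications*, history of allergies".

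SAP 8.1.4 gives the only derivation of the variable. Its Complication row reads "No (if status of medical history is 'Ongoing'), Yes (if otherwise". In the same table, the Drinking Status and Smoking Status rows read "No (if 'Never'), Yes (if otherwise". The output is fixed by the sentence below the table: "Demographic and other baseline characteristics will be summarized and listed on the SAF". SAP 8.1.5 adds a separate listing: "Medical history and allergic history will be listed on the SAF".

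**The concern.** A complication at baseline would ordinarily mean a condition the subject has on entering the study. The rule gives No to exactly the subjects who have one. It gives Yes to subjects whose conditions have ended and, read literally, to subjects with no medical history at all.

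SAP section 1 gives the SAP precedence over the protocol on statistical detail, so this is the operative rule for a summary the protocol requires. A programmer who follows it exactly produces a baseline row and listing with the categories reversed. A programmer who silently corrects it produces output that departs from the SAP without a record. SAP section 10 reports no changes from the protocol's analysis, so nothing there alerts either of them.

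**Working it through.** The documents give no figure for this row, so there is nothing to reproduce. The check has two parts: the direction of the rule, and what the rule does to the table.

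**Direction**

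1. The protocol keeps complications apart from medical history in both 9.1 and 13.4.1. If the word meant past conditions, the separate item would add little.
2. Protocol 9.2.5.2, on the relationship of an adverse event to the product, says: "The assessment will include such factors as the natural course of complications or underlying diseases". There a complication is something whose course could explain an event during the study, which fits a current condition and not one that has resolved.
3. The SAP ties the row to the ongoing status of the medical history, which is the natural marker of a concurrent condition.
4. In the Drinking and Smoking rows, No marks absence of the characteristic. In the Complication row, No marks presence.
5. Suppose instead that the word meant past conditions. The literal 'otherwise' would still give Yes to a subject with no record, so that meaning does not rescue the rule.
6. No other section gives a different derivation. Protocol 9.2.1.1 lists medical history without a complications item, and SAP 7.1.1.2 covers only the coding dictionary.

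**Effect on the row**

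Inputs: N = 16 planned, 4 per group (Protocol 6.1, SAP 3.4). Assumed, because the documents do not give them: k subjects with an ongoing condition and m subjects with any medical-history record. A subject counts as ongoing if any record is ongoing, except in reading 3. The intended Yes count is k.

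*Reading 1: 'otherwise' covers every other subject, including those with no history.* Yes as written = 16 − k.

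| k | Yes as written | Yes intended | Difference, 16 − 2k |
|---|---|---|---|
| 0 | 16 (100%) | 0 (0%) | 16 |
| 1 | 15 (93.8%) | 1 (6.3%) | 14 |
| 2 | 14 (87.5%) | 2 (12.5%) | 12 |
| 3 | 13 (81.3%) | 3 (18.8%) | 10 |

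The counts agree only at k = 8, and even then all 16 subjects carry the wrong label, because the rule gives the exact complement.

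The protocol asks for the calculation by group. With 4 per group and j ongoing in a group, Yes as written = 4 − j. For j = 0 the row shows 4 (100%) instead of 0. For j = 1 it shows 3 (75%) instead of 1 (25%). For j = 2 it shows 2 (50%) either way, with the wrong subjects in each category.

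*Reading 2: the rule applies only to subjects with a record.* Yes as written = m − k. With m = 4, for k = 0, 1, 2, 3 this gives 4, 3, 2, 1 instead of 0, 1, 2, 3. With m = 0 both rules give 0 and there is no error.

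*Reading 3: any record that is not ongoing gives Yes.* Yes = the number of subjects with at least one resolved record, which the documents do not give. A subject with both ongoing and resolved records would be Yes; one with only ongoing records would be No.

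**Reach**

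The food-effect ANOVA in SAP 8.4.2 uses sequence, subject within sequence, period (Periods 1 to 4 only) and meal condition. The analysis sets in SAP section 5 depend on dosing and evaluable PK data. The adverse-event summaries in SAP 8.3.1 do not use the flag. The causality assessment in Protocol 9.2.5.2 is an investigator's judgement and does not draw on it either.

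**The case against.** The strongest objection is that this is a drafting slip on one descriptive row of a study in healthy volunteers. No estimate, interval or safety conclusion depends on it. The source records are listed separately under SAP 8.1.5, and SAP section 1 provides for quality control and a check of the outputs, so a table reporting a complication in every healthy volunteer would probably be noticed. This stands as a limit on the consequence. It does not correct the rule: a check of the output against the SAP as written would confirm the reversed table.

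The percentages out of 16 can also be challenged, because Protocol 13.4.1 asks for results by group and SAP 8.1.4 mentions no pooled column. That is fair. The pooled figures are illustrations, and the by-group values move in quarters.

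A third point is that the size rests on unknown counts. Under reading 2, if no subject has any medical-history record, the row is correct by accident. That also stands, so the misreporting is conditional on the reading and on the records.

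Last, the term is never defined and the medical-history form is not among the documents, so the intended meaning is an inference. It is one, but it rests on several places that agree, and nothing in the documents points the other way.

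**Conclusion.** The concern holds. As written, SAP 8.1.4 reverses the Complication coding relative to the protocol's use of the term and to the other rows of the same table, and it does not say how to code a subject with no record or with mixed records. The conclusion on direction rests on taking a complication to be a concurrent condition.

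Under the literal reading (reading 1) every subject is placed in the wrong category. The pooled error in the count is 16 − 2k, at its largest when no one has an ongoing condition. Under the narrower reading 2 the error is limited to subjects with a medical-history record and vanishes if there are none. The effect stays within one baseline row and its listing. This is a minor error in consequence, but a definite one that should be corrected.

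**What to change.** Reword the row in SAP 8.1.4 so that Complication is Yes if any medical-history record has status Ongoing, and No otherwise, including subjects with no medical history. This reverses the labels and also settles subjects with no record and subjects with both ongoing and resolved records.

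If the row has already been produced, compare it subject by subject with the medical-history listing, re-run it if needed, and record the correction.

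The cost is one line in the SAP and one derived variable to re-run. No new data are needed, and only the baseline table and listing that carry this row change.

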8.1.5. Medical History and Allergic History

Medical history and allergic history will be listed on the SAF.

8.1.6. Prior or Concomitant Medications

Prior and concomitant medication will be listed on the SAF.

8.2. Efficacy Assessments

N/A

8.3. Safety Assessments

Safety assessments will be made on the SAF population.

8.3.1. Adverse Events

Overall summary for the following will be conducted by treatment.

- Subjects with at least one AE
- Subjects with at least one adverse drug reaction
- Subjects with at least one SAE
- Subjects with at least one serious adverse drug reaction
- Subjects with at least one AE leading to discontinuation of investigational product
- Subjects with AE leading to death

The following summaries also will be conducted by treatment.

- AEs by SOC and PT
- Adverse drug reactions by SOC and PT
- AEs by SOC, PT and severity

Each of the summaries will be done at the subject level - multiple occurrences of the same event within a subject will be counted once in the summaries by SOC and PT; multiple occurrences of the same event within a subject will be counted once in the maximum severity category (severe > moderate > mild) and/or maximum drug relationship category (reasonable possibility/no reasonable possibility) and/or the earliest duration.

All AEs will be listed.

8.3.2. Laboratory Tests

Absolute values and changes from baseline, except for urinalysis will be summarized descriptively by group and scheduled visit.

For urinalysis, number and percentage will be presented. Shift tables will present the changes in clinically relevant categories from baseline to each scheduled post-baseline visit by group and scheduled visit.

Below is a list of the laboratory test.

Laboratory Test	Parameters
Hematology	Hemoglobin, hematocrit, red blood cell count, white blood cell count, platelet count, MCH, MCHC, MCV, differential white blood count
Biochemistry	Na, K, Cl, Ca, inorganic phosphorus, urea nitrogen, creatinine, uric acid, total bilirubin, direct bilirubin, ALT, AST, γ -GTP, ALP, LDH, CK, amylase, total cholesterol, triglycerides, LDL-C, HDL-C, total protein, albumin, glucose
Coagulation test	Prothrombin time, activated partial thromboplastin time
Urinalysis	Qualitative tests (pH, specific gravity, protein, glucose, occult blood, urobilinogen, bilirubin, ketones), sediment(listing only)

All data including clinically relevant flagged will be listed. Any BLQ data will be treated as 0 in summary statistics.

8.3.3. Vital Signs

Absolute values and changes from baseline will be summarized for the following parameters by treatment and scheduled time point.

- Systolic Blood Pressure (mmHg)
- Diastolic Blood Pressure (mmHg)
- Pulse Rate (bpm)
- Body Temperature(°C)

All data will be listed.

8.3.4. 12-Lead ECGs

Absolute values and changes from baseline will be summarized for the following parameters by treatment and scheduled time point.

- Heart Rate (beats/min)
- PR (msec)
- RR (msec)
- QRS (msec)
- QT (msec)
- QTcF (msec)

The percentage of subjects with 12-lead ECG values outside pre-defined limit will be summarized by treatment and scheduled time point.

All data (including overall evaluation) will be listed.

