Systolic and diastolic blood pressure will be measured after at least a 5-minute rest in a lying position. One measurement will be taken for each time point. The measurements will be taken in the same arm throughout the study period, in principle.

If the timing of measurement is the same as that of blood sampling, it should be conducted before blood sampling.

Confidential

Time points

Screening	No specifications ^{b)}
Day -1 (hospitalization)	No specifications ^{b)}
Day 1	Pre-dose, and 1 hour post-dose
Day 2	24 hours post-dose
Day 3	Pre-dose, and 1 hour post-dose
Day 4	24 hours post-dose
Day 5	Pre-dose, and 1 hour post-dose
Day 6	24 hours post-dose
Day 7	Pre-dose, and 1 hour post-dose
Day 8	24 hours post-dose ^{b)}
Day 9 (discharge)	48 hours post-dose ^{b), c)}
Day X ^{a)} (hospitalization)	No specifications ^{b)}
Day X+1 ^{a)}	Pre-dose, and 1 hour post-dose
Day X+2 ^{a)}	24 hours post-dose ^{b)}
Day X+3 ^{a)} (discharge)	48 hours post-dose ^{b), c)}
End-of-study assessment or withdrawal assessment	No specifications ^{b)}

a) X = Day of hospital admission in period V

b) To be performed in the fasting state (before breakfast).

c) In the C: Dosing 4 hours after low-fat meal and F: Dosing 4 hours after light meal, the measurement is conducted 46 hours post-dose.

(3) 12-lead ECG

After at least a 5-minute rest in a lying position, a 12-lead ECG will be recorded at the time points shown in the table below. The investigator (or subinvestigator) will record the date and time of measurement, heart rate, QTcF interval, PR interval, QT interval, RR interval, QRS interval, and findings in the CRF.

If the timing of measurement is the same as that of blood sampling, it should be conducted before blood sampling.

Time points

Screening	No specifications ^{b)}
Day -1 (hospitalization)	No specifications ^{b)}
Day 1	Pre-dose, and 1 hour post-dose
Day 2	24 hours post-dose
Day 3	Pre-dose, and 1 hour post-dose
Day 4	24 hours post-dose
Day 5	Pre-dose, and 1 hour post-dose
Day 6	24 hours post-dose
Day 7	Pre-dose, and 1 hour post-dose
Day 8	24 hours post-dose ^{b)}
Day 9 (discharge)	48 hours post-dose ^{b), c)}
Day X ^{a)} (hospitalization)	No specifications ^{b)}
Day X+1 ^{a)}	Pre-dose, and 1 hour post-dose
Day X+2 ^{a)}	24 hours post-dose ^{b)}
Day X+3 ^{a)} (discharge)	48 hours post-dose ^{b), c)}
End-of-study assessment or withdrawal assessment	No specifications ^{b)}

a) X = Day of hospital admission in period V

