13.3 Data Handling

The data will be handled as described below, except for cases determined in the sponsor's data review meeting or at the meeting for the handling of drug concentration data. The handling of the safety and drug concentration data will be specified in the Statistical Analysis Plan or the Clinical Study Report.

(1) Handling of PK data

The acceptance time range for each blood sampling timepoint for determining the plasma drug concentrations will be specified in the Statistical Analysis Plan. The sponsor will judge the handling of the following data, as to whether or not to include them in the tabulation and analysis of the drug concentrations: (1) data that was collected from a blood specimen drawn outside of the acceptance time range; (2) data for which the plasma drug concentration was unmeasurable; and, (3) data for which a protocol deviation occurred, such as non-compliance with plasma collection procedures. The handling of data will be decided at the data review meeting or at the conference for the handling of PK data.

(2) Handling of analysis data for each time point

The acceptable time range for each measurement time point will be specified in the Statistical Analysis Plan, and the data collected within the time range will be used. Data will not be imputed by data collected outside the time range. If multiple data exist within the same time range for one assessment item, the data collected later will be used.

(3) Handling of unmeasurable data and reference data in laboratory tests

If unmeasurable or reference data are obtained due to specimen problems, etc., they will be handled as missing data.

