7.1.2.2. Laboratory Tests

Values for out of pre-defined clinically relevant will have clinically relevant values flagged set (L=Lower than normal range, H=Higher than normal range or A=Abnormal).

7.1.2.3. 12-Lead ECG

(1) Criteria for pre-defined limit

12-lead ECG:

- QTcF > 500msec
- $500 \geq QTcF > 480$ msec
- $480 \geq QTcF > 450$ msec
- QTcF ≤ 450 msec
- Change from baseline in QTcF > 30 msec
- Change from baseline in QTcF > 60 msec

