7.2. Analysis Visit Definitions

(1) Non-PK related

The date of the first dose of investigational product is defined as Day 1.

Excepted for laboratory, baseline will be the last observed value of the parameter of interest prior to the first intake of investigational product by each treatment period (this includes unscheduled visits). For laboratory, baseline will be the last observed value of the parameter of interest prior to the first intake of investigational product (this includes unscheduled visits).

No analysis visit window will not be perfomed for safety evaluation.

(2) PK related

The allowable time window will be the following.

Plasma PK sampling

Nominal Time Point	Window
Predose	Within 60 min before dosing
0.083 h after dosing	Nominal time point \pm 1 min
0.25, 0.5, 0.75, 1, 1.5, 2, 4, 6, 8, 10, 12 h after dosing	Nominal time point \pm 5 min
24, 36 h after dosing	Nominal time point \pm 15 min
48 h* after dosing *Following the dosing 4 hours after meals, blood sampling is conducted 46 h after dosing	
Blood sampling 46 h after dosing	[Period I, II, and III] 45~47 h after dosing and within 60 min before the dosing in the next period [Period IV and V] 45~47 h after dosing
Blood sampling 48 h after dosing	[Period I, II, and III] 47~50 h after dosing and within 60 min before the dosing in the next period [Period IV and V] 47~50 h after dosing

Urine PK sampling

Nominal Time Point	Window
Predose	Within 60 min before dosing
Voluntary Urine	—
Forced micturition at 24 h after dosing	Nominal time point \pm 30 min

Nominal Time Point	Window
Forced micturition at 48* hours post-dose * Forced micturition at 46 h post-dose for subjects dosed 4 h after meals	
Forced micturition at 46 h after dosing	[Periods I, II, and III] 45~47 h after dosing and within 60 min before the dosing in the next period [Periods IV, V] 45~47 h post-dose
Forced micturition at 48 h after dosing	[Periods I, II, and III] 47~50 h after dosing and within 60 min before the dosing in the next period [Periods IV, V] 47~50 h post-dose

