9.3. Analysis Visits to Report

(1) Non-PK related

Analysis Visit	Analysis Time Point	Apply to	Laboratory Tests	Vital Signs	12-Lead ECGs
Screening		X		X	X
Day -1		X (baseline)		X	X
Day 1	Pre-dose			X (baseline)	X (baseline)
Day 1	1 hour			X	X
Day 2	24 hours			X	X
Day 3	Pre-dose			X (baseline)	X (baseline)
Day 3	1 hour			X	X
Day 4	24 hours			X	X
Day 5	Pre-dose	X		X (baseline)	X (baseline)
Day 5	1 hour			X	X
Day 6	24 hours			X	X
Day 7	Pre-dose			X (baseline)	X (baseline)
Day 7	1 hour			X	X
Day 8	24 hours			X	X
Day 9	46 hours	X		X	X
Day 23		X		X	X
Day 24	Pre-dose			X (baseline)	X (baseline)
Day 24	1 hour			X	X
Day 25	24 hours			X	X
Day 26	48 hours	X		X	X
Follow up		X		X	X

Screening, unscheduled visits, retests (same visit number assigned) will not be displayed in by-visit summary tables, but will be included in the data listings.

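### The by-condition QTcF outlier table counts scheduled time points only, so it misses exceedances seen only on unscheduled or repeat ECGs and gives no per-subject count

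*SAP*

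**What the plan says.** SAP 7.1.2.3 sets the ECG limits: QTcF bands cut at 450, 480 and 500 msec, and change from baseline above 30 msec and above 60 msec ("Change from baseline in QTcF > 60 msec"). SAP 8.3.4 says how they are reported: "The percentage of subjects with 12-lead ECG values outside pre-defined limit will be summarized by treatment and scheduled time point". The same section adds "All data (including overall evaluation) will be listed".

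SAP 9.3 governs the by-visit tables: "Screening, unscheduled visits, retests (same visit number assigned) will not be displayed in by-visit summary tables, but will be included in the data listings".

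SAP 7.2 treats unscheduled readings differently when it defines baseline. For ECG, baseline is the last value "prior to the first intake of investigational product by each treatment period (this includes unscheduled visits".

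Protocol 9.2.5.1(3) schedules ECGs on each dosing day ("Pre-dose, and 1 hour post-dose") and at 24 h. It adds a 48 h ECG (46 h after conditions C and F) at the two discharges, Day 9 and Day X+3. Neither document plans a row for the worst post-dose value or for any exceedance within a period.

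**The concern.** Limits of this kind exist to catch extreme values. An unscheduled ECG is often taken because something prompted it, and a repeat often follows an abnormal first tracing. Both are barred from the table built to show extremes. The bar is also one-sided: an unscheduled ECG before dosing can serve as the reference for a change score, but one taken after dosing cannot count as an outcome.

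A second gap does not depend on unscheduled ECGs. A reader comparing meal conditions wants to know how many subjects exceeded a limit at any point after that dose. Separate percentages at 1 h and 24 h do not answer this.

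At stake is the by-condition count of subjects with a QTcF exceedance. Leaving out post-dose readings can only lower that count.

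**Working it through.** The documents give no outlier rate to reproduce, and SAP 3.4 states that the sample size is not based on a calculation. The check is therefore a comparison of texts with three short counts.

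**1. Where a post-dose exceedance seen only on an unscheduled or repeat ECG would appear**

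| Output | Restriction | Shown? |
|---|---|---|
| QTcF limit table (SAP 8.3.4) | Scheduled time points; retests and unscheduled visits excluded by SAP 9.3 | No |
| ECG descriptive statistics (SAP 8.3.4) | Same | No |
| Adverse event tables by treatment (SAP 8.3.1) | No visit restriction; events assigned to a condition by dosing date and time (SAP 7.1.2.1) | Only if reported as an adverse event |
| ECG listing (SAP 8.3.4, 9.3) | None | Yes, by subject, without a count |

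The adverse event route depends on Protocol 9.2.5.2(2), under which a clinically significant abnormal finding is handled as an adverse event. Crossing a numerical QTcF limit is not by itself one of the criteria there. The same section says that when a symptom is the reported event, the related laboratory abnormality is not reported separately. It does not say whether this covers ECG findings.

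**2. What a table by time point can say about subjects**

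If x1 of n subjects exceed a limit at 1 h and x2 at 24 h, the number exceeding it at either time lies between max(x1, x2) and min(n, x1 + x2). As an illustration, take n = 16 and x1 = x2 = 1:

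- lower bound: 1/16 = 6.25%
- upper bound: 2/16 = 12.5%

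The planned table cannot tell these apart.

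**3. Weight of one omitted subject**

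With 16 subjects in a condition (SAP 3.4), one omission changes 1/16 = 6.25% to 0/16 = 0%. To the one decimal place set in SAP 9.1, 6.25% prints as 6.3%. This is the weight of a single subject, not an estimate of bias.

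**4. Which window a per-subject row should use**

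Scheduled post-dose ECGs, counted from Protocol 9.2.5.1(3):

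| Period | Up to the next dose | Up to the 46/48 h assessment |
|---|---|---|
| I, II, III | 1 h, 24 h, next pre-dose = 3 | 1 h, 24 h, next pre-dose = 3 |
| IV | 1 h, 24 h, Day 9, Day X, Day X+1 pre-dose = 5 | 1 h, 24 h, Day 9 = 3 |
| V | No next dose; to end of study 1 h, 24 h, Day X+3, final visit = 4 | 1 h, 24 h, Day X+3 = 3 |

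Each of A to D falls once in each of Periods I to IV across the four equal groups. A window running to the next dose would therefore give them (3 + 3 + 3 + 5)/4 = 3.5 scheduled ECGs per subject, against 4 for the Period V condition. Ending at the 46/48 h assessment gives 3 in every period. The pre-dose ECG on Days 3, 5 and 7 can stand as that assessment because Protocol 9.2.4.1 equates the pre-dose blood sample on those days with 48 h after the previous dose (46 h after C).

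**The case against.** The case for leaving the plan alone has real force. Clinically significant findings become adverse events and are tabulated by treatment. Every ECG is listed, and 16 subjects can be read line by line. Protocol 13.4.3(3) asks only for descriptive ECG statistics, so the outlier table already goes beyond it. Safety is a secondary objective, and Protocol section 1(3) cites a separate QT/QTc study. No symptom-driven ECG is scheduled, and neither document says that any was done.

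This limits the point to one table and a low priority. It does not supply the missing count.

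Three stronger readings are tempting, and the documents do not support them:

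- **A reader might infer that such a value never reaches any by-condition safety summary.** It can do so through the adverse event tables, if it is itself reported as an event.
- **A reader might infer from Protocol 13.3(2) that a normal repeat replaces a prolonged first reading.** That rule says: "If multiple data exist within the same time range for one assessment item, the data collected later will be used". It relies on time ranges to be set in the SAP. SAP 7.2 appears to set none for safety, although its sentence on this is garbled. SAP section 1 overrides the protocol on analysis detail, and SAP 9.3 drops the retest, so a prolonged first scheduled reading stays in. What remains is a mismatch in documentation, because SAP section 10 declares no changes from the protocol.
- **A reader might infer that nothing is recorded after 24 h in Periods I to III.** The next period's pre-dose ECG is recorded at about 46 to 48 h. SAP 9.3 labels it only as the next period's baseline.

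An added row also has its own weakness: a maximum over more readings is more likely to cross a limit. That supports a bounded window and keeping the planned table, not omitting the row.

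**Conclusion.** The point holds for the QTcF outlier table and no further. As written, that table omits any exceedance seen only on an unscheduled or repeat ECG, and it cannot give the number of subjects per condition with any post-dose exceedance. The first gap has unknown size: zero omitted subjects if there were no such ECGs, otherwise 6.25 percentage points per omitted subject, always downward. The second gap exists whatever ECGs were taken, although it matters only if exceedances occur at more than one time point within a condition.

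This assumes that all 16 subjects contribute to each condition and that the SAP 8.3.4 limit table counts as a by-visit table under SAP 9.3. It is a low-priority improvement and does not affect the primary food-effect analysis.

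**What to change.** In SAP 8.3.4, add one row per condition labelled 'any post-dose ECG'. For each subject it takes the worst QTcF and the largest change from that period's baseline, over all scheduled, unscheduled and repeat ECGs in a fixed window.

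- **Window:** from dosing to the 46/48 h assessment in every period. In Periods I to III that assessment is the next period's pre-dose ECG; in Periods IV and V it is the discharge ECG.
- **Exemption:** state that the SAP 9.3 exclusion of unscheduled visits and retests does not apply to this row.
- **Keep:** the table by scheduled time point, unchanged, beside it.

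The cost is one table row and a sentence or two in the SAP, because the data are already collected and listed. If the database is already locked, Protocol 13.5 requires the addition and its reason to be recorded in a revised SAP and the study report. The downside is that subjects with more repeat ECGs have more chances to exceed a limit, so the new row should be read with the scheduled table.
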